LACOSAMIDE EFFECTS ON ALCOHOL SELF ADMINISTRATION AND CRAVING IN HEAVY DRINKERS

ClinicalTrials.gov number: NCT03271528

Protocol Version Number: 3.12 **Protocol Version Date:** 3.11.19

Sponsor: NIAAA/NIH

Principal Investigator: [name].

[contact]

E-mail: [contact]

CONFIDENTIAL

This document is confidential and the property of Boston Medical Center. No part of it may be transmitted, reproduced, published, or used by other persons without prior written authorization from the study sponsor.

TABLE OF CONTENTS

1	List c	of Abbreviations	. 3
2	Proto	col Summary	. 3
3	Back	ground/Rationale & Purpose	۷.
	3.1	Background Information	۷.
	3.2	Rationale and Purpose	. 7
4	Objec	ctives	. 7
	4.1	Study Objectives	. 7
	4.2	Study Outcome Measures	. 7
		4.2.1 Primary Outcome Measures	. 7
		4.2.2 Secondary Outcome Measures	. 7
5	Study	/ Design	. 8
6	Poten	itial Risks and Benefits	٤ .
	6.1	Risks	٤ .
	6.2	Potential Benefits	
	6.3	Analysis of Risks in Relation to Benefits	13
7	Study	Subject Selection	14
	7.1	Subject Inclusion Criteria	
	7.2	Subject Exclusion Criteria	
8	Study	Intervention	15
9	Study	Procedures	16
10		ssment of Safety and Data Safety Monitoring Plan (DSMP)	
		Definitions	
	10.2	Safety Review	20
		Reporting Plans	
		Stopping Rules	
11		Handling and Record Keeping	
		Confidentiality	
		Source Documents	
		Case Report Forms	
		Study Records Retention	
12		tical Plan	
		Study Hypotheses and Proposed Analyses	
		Sample Size Determination	
		s/Protection of Human Subjects	
		nture References	26
15.	Apne	endix A: Schedule of Events	32

1 List of Abbreviations

Abbreviation	Abbreviation definition
Alcohol Use Disorder	AUD

2 Protocol Summar	у
Title:	Lacosamide effects on alcohol self administration and craving in heavy drinkers.
Population:	The present study will involve 112 men and women aged 21 to 55 who exceed safe levels of drinking. Women and minorities who meet the study criteria will be eligible to participate. No vulnerable populations are being targeted for inclusion in this study
Intervention:	Eligible subjects will be titrated to a target dose of 300mg of lacosamide (or a matched placebo) over a 7-day period. A riboflavin tracer will be added to each capsule to serve as an objective measure of medication adherence. Subjects will receive a single 150 mg dose of lacosamide on day 8. Subjects will take study medication by mouth. Subjects will receive alcohol in the laboratory on day 8 in an alcohol craving challenge. Subjects will be presented with four drinks, each mixed to raise their BAL 0.015g/dl. They will be told that they can either consume the desired number of drinks over the following 60 minutes or they will receive the equivalent in a cash reward. This procedure will be repeated with an additional 4 drinks after 60 minutes has elapsed. Subjects will serve as their own controls. The intervention will be repeated with a placebo/lacosamide after a washout period. The order of lacosamide and placebo dosing will be randomized.
Objectives:	The specific objective of this study is to determine whether lacosamide, a novel anticonvulsant that is FDA-approved for treating partial seizures, has effects on alcohol craving and consumption. This medication is a promising candidate that has unique actions on voltage-gated sodium channels and may have inhibitory effects on collapsin response mediator protein-2 (CRMP-2). Testing the effects of lacosamide on drinking is a compelling opportunity that is consistent with the mission of NIAAA to evaluate the efficacy of re-purposed compounds with novel mechanisms that have the potential to treat AUD. If successful, this study could lead to a phase II randomized controlled trial to test lacosamide as a treatment for AUD. The specific goal of this study is to evaluate the effects of lacosamide on drinking and craving among heavy drinkers in a human laboratory using an alcohol self-administration

paradigm.

This is a double-blind, randomized, placebo-controlled, Design/Methodology: crossover design trial that will test the effect of lacosamide on alcohol self-administration and craving following a priming dose of alcohol. An established human laboratory selfadministration procedure will be followed. Each subject will complete 5 clinic visits over a period of up to 44 days of participation. Study participation is comprised of a baseline assessment, randomization visit, alcohol self administration Trial 1, an assessment visit to verify continued eligibility and dispense medication, and a second alcohol self-administration Trial. The volume of alcohol consumed during alcohol challenge trials 1 and 2 will be used to test the effect of lacosamide on alcohol consumption. Craving measures (AUO and VAS) collected during the self-administration trials will be used to test the effect of lacosamide on alcohol craving. The entire study will take 24 months to complete. **Total Study Duration: Subject Participation** Each subject's length of participation will be up to 44 days.

3 Background/Rationale & Purpose

3.1 Background Information

Duration:

Current models of care for treating Alcohol Use Disorder (AUD) include both behavioral therapies and pharmacotherapy¹. Although pharmacotherapy for AUD in the US has been available since 1948 when disulfiram was approved, options for treatment are limited as there are only four medications which have been approved by the FDA for treating AUD. Disulfiram, naltrexone, acamprosate, and long-acting naltrexone have all shown promise as agents to treat AUD² but no single medication has proven to be effective across the heterogeneous groups of people with AUD³. Movement towards models of personalized care and pharmacogenetic treatment matching⁴⁻⁵ hold some promise for improving AUD treatment outcomes, but the limited number of unique mechanisms of action of the currently approved drugs presents a challenge to implementing this model of care. Unfortunately, few novel compounds to treat AUD progress to phase II trials, and developing novel compounds is both costly and timeconsuming⁶. One pathway of drug development efforts has been focused on re-purposing FDA approved medications that have promising mechanistic effects⁷ and some success has been achieved in using this strategy with anticonvulsants⁸. Identification of additional drugs with unique mechanisms of action that are found to reduce alcohol consumption could expand the treatment options and further the goal of personalized care for AUD. The overarching goal of our research is to identify agents with unique mechanisms that hold promise for treating AUD. The specific objective of this study is to determine whether lacosamide, a novel anticonvulsant that is FDA-approved for treating partial seizures, has effects on alcohol craving and

Alcohol Use Disorder as a national health problem

More than 16 million adults suffer from Alcohol Use Disorder (AUD) in the United States⁸. The economic burden of this is estimated to be 249 billion dollars and approximately 88,000 Americans die from alcohol-related causes each year⁹. Untreated AUD is associated with an increased risk of accidents, injuries, suicide, and worsening of other health comorbidities¹⁰ and it is the fourth most preventable cause of death in the US⁹. Treating addiction more effectively has become a priority of national importance and the Surgeon General has urged researchers to undertake testing of new treatments to combat addiction¹¹. The present study is intended to answer the call for accelerating drug development for AUD by exploring the potential to repurpose an existing drug as a treatment for AUD⁶⁻⁷.

Rationale for developing lacosamide as an agent to treat AUD

Lacosamide is a D-serine analogue that is approved for use as a therapeutic agent for treatment of partial seizures¹². In contrast to other anticonvulsant agents, this drug decreases seizure activity, in part, by enhancing slow sodium channel inactivation¹³⁻¹⁴. The administration of lacosamide to either mice (C57Bl/6J) or rats (Long Evans) has been shown to significantly reduce their intake of alcohol in a model of 'excessive' drinking¹⁵. This finding is of interest because the predominance of evidence suggests that in addition to its action on sodium channels, this anticonvulsant binds to and inhibits the activity of collapsin response mediator protein-2 (CRMP-2)¹⁶⁻¹⁸. Alcohol consumption in mice that had knockdown of CRMP-2 within the nucleus accumbens (a mesolimbic structure that regulates alcohol consumption and seeking behaviors) was decreased from levels seen in control animals¹⁵. This finding implicates CRMP-2 as having a role in the regulation of alcohol consumption.

Based on the finding that lacosamide decreases alcohol consumption in rodents, we plan to test our hypothesis that this drug will have similar effects on the self-administration of alcohol by human subjects. Confirmation of this hypothesis would be of particular significance because CRMP-2 is a downstream target of the mammalian target of rapamycin complex 1 (mTORC1)¹⁵, Several studies implicate mTORC1 in the development of the neuroadaptations that are involved in the seeking and consumption of a wide range of abused substances including alcohol²⁶. Administration of the mTORC1 antagonist rapamycin into the nucleus accumbens has been shown to decrease alcohol consumption and seeking behavior in rats²¹. In addition, systemic and intra-amygdalar micro-infusion of this drug appears to disrupt memories of alcohol-related cues and thereby suppresses behavior in rodent models of drinking and relapse²². These results suggest that rapamycin or other drugs with similar mechanistic effects may have efficacy as medications for the treatment of AUD through a mechanism that is not targeted by any medications currently used to treat AUD.

Rapamycin (sirolimus) is approved for use as an immunosuppressant agent, but it can produce toxic effects including myelosuppression and leukoencephalopathy which would constitute an unacceptable risk in an AUD population. Testing of medications that act on targets downstream of mTORC1 that are less toxic than rapamycin may prove to be a useful approach in the development of drugs for the treatment of AUD through this novel mechanism. The findings of Liu and colleagues suggest that CRMP-2 may be an important downstream mTORC1 target for medications that will produce reductions in alcohol consumption because this protein may play a role in the neuroplastic changes associated with the development of excessive drinking. These changes may be related to alcohol-induced changes in the characteristics of neuronal

dendritic spines and related alterations in the activity of select neurotransmitter systems²³⁻²⁵. Liu and his co-investigators reported that the mTORC1 antagonist rapamycin blocks alcohol mediated increases in CRMP-2 polysomal messenger RNA within the nucleus accumbens. Indeed, CRMP-2 protein levels within the nucleus accumbens of the rat have been found to be elevated after episodes of alcohol consumption. CRMP-2 stabilizes microtubules within dendrites and may promote neurite outgrowth. Interestingly, lacosamide has been shown to block CRMP-2-induced neurite complexity in cultured brain cortical cells, suggesting a possible mechanism through which this medication may block alcohol-induced changes in neuroplasticity²⁶.

Lacosamide fits the description as a medication that modulates the activity of a downstream target protein of mTORC1 that appears to regulate alcohol consumption in rodent models. In contrast to rapamycin, this drug has been found in clinical trials to be well tolerated, producing dose related adverse effects including dizziness, nausea, and diplopia that were in the mild to moderate range²⁷ and that are common adverse effects produced by almost all anticonvulsant drugs. When used as monotherapy, a small percentage of patients had to discontinue lacosamide therapy because of the occurrence of rash, dizziness, headache, somnolence and elevations in liver function tests (i.e.γ-glutamyl transferase and aspartate aminotransferase)²⁸. There are two post-marketing reports of heart block occurring in patients who were treated with a combination of lacosamide and the beta-adrenergic receptor antagonist metoprolol²⁹. Major concerns with the occurrence of severe skin rash, hepatoxicity, suppression of white blood cell production, or weight gain that are associated with the use of certain other anticonvulsant medications have not been reported to be a problem in patients treated with lacosamide.

Treatment with the broad spectrum anticonvulsants topiramate and zonisamide, which are reported to reduce alcohol consumption in AUD subjects, is associated with the occurrence of deficits in cognitive functioning including impairment of verbal fluency and working memory³⁰. These adverse cognitive effects may limit their acceptability for the treatment of AUD for many individuals. The administration of lacosamide as compared to topiramate, when these drugs are used as adjunctive agents, may be less likely to adversely affect cognitive function in epilepsy patients³¹. Lacosamide also appears to be less likely than the anticonvulsant carbamazepine to impair performance on a wide range of neuropsychological tests³². In a study of the effects of lacosamide in patients with partial seizures, no significant differences in COWAT scores were found between weeks 1 and 28 of treatment with this drug when administered in doses ranging between 100 to 400 mg per day³³. Lacosamide was found to produce a significant, but modest, reduction in WAIS-III Digit Span scores (a test of working memory) collected for these patients. We believe that lacosamide is a promising agent for drug development given the novel mechanism of action, positive findings in animal models, and an acceptable safety profile.

In this study, the effects of lacosamide on cravings will also be assessed. This is important because cravings that follow alcohol consumption may be important factors in motivating drinking³⁴⁻³⁶. The effects of anticonvulsants on these factors in the context of alcohol challenge and self-administration studies have not been extensively examined. In an alcohol self-administration study testing zonisamide, we found that reductions in craving occurred in association with reduced alcohol self-administration³⁷. These results are similar to those showing that naltrexone administration leads to significant corresponding reductions in alcohol self-administration and craving scores³⁸. Understanding the effect of lacosamide on craving and stimulant effects of alcohol may inform our understanding of how lacosamide impacts drinking.

This study will be conducted in compliance with the protocol, applicable regulatory requirements, and BMC/BU Medical Campus Human Research Protection policies and procedures.

3.2 Rationale and Purpose

This study holds significant innovation as there is mounting evidence that medications that act on targets downstream of mTORC1 have the potential to decrease craving and consumption, but no medications have been developed to date to take advantage of this novel mechanistic approach. Two medications which impact the mTORC1 pathway, lacosamide and rapamycin, have been tested in rodent models and both medications have been shown to reduce alcohol consumption^{15,21}. Rapamycin is not a promising candidate for drug development due to the potential for serious adverse effects, but lacosamide is promising given the findings from animal models, the tolerable safety profile, and the low incidence of cognitive adverse effects relative to other anticonvulsants used to treat AUD. To date, there have been no controlled studies testing lacosamide in human drinkers that either have been published or registered with Clinicaltrials.gov. The study answers the call for accelerating the development of medications for AUD by testing a commercially-available and well-tolerated agent at a fraction of the cost of developing novel therapies. If successful, this study could lead to a phase II randomized controlled trial to test lacosamide as a treatment for AUD.

4 Objectives

4.1 Study Objectives

The specific objective of this study is to determine whether lacosamide has effects on alcohol craving and consumption. This medication is a promising candidate that has unique actions on voltage-gated sodium channels and may have inhibitory effects on collapsin response mediator protein-2 (CRMP-2). Testing the effects of lacosamide on drinking is a compelling opportunity that is consistent with the mission of NIAAA to evaluate the efficacy of re-purposed compounds with novel mechanisms that have the potential to treat AUD.

4.2 Study Outcome Measures

4.2.1 Primary Outcome Measures

The primary outcomes are alcohol consumption and cravings during the alcohol self-administration trials. Drinking volume during the alcohol self-administration will be measured to evaluate the effects of lacosamide vs. placebo on the rate of alcohol consumption after a priming drink. Alcohol craving will be measured using the Visual Analog Scale (VAS) and the Alcohol Urge Questionnaire (AUQ)³⁹ during the lacosamide self-administration trial. These self-report measures of craving will be used to evaluate the effect of lacosamide on craving vs. placebo.

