12.1 Study Hypotheses and Planned Analyses

For our primary outcomes, separate analyses will be conducted on data collected during the Priming and Self-Administration periods of the test session.

Hypothesis	Planned Analyses
1. Subjects will consume	The volume of alcohol consumed during alcohol challenge trials 1 and
less alcohol during an	2 will be used to test the effect of lacosamide on alcohol consumption.
alcohol self-administration	We will use a mixed models repeated measures approach to test for
trial when receiving	differences between alcohol consumed between the lacosamide and
lacosamide compared to	placebo self-administration trials ⁶¹⁻⁶² . This data will be divided into
when they are receiving	first and second-hour blocks of self-administration. Within-subject
placebo.	factors for this analysis will include treatment and Time Block. Trial
	order will be used as covariate in these analyses to allow evaluation as
	to whether the order of treatments had a significant effect on the
	outcome. Appropriate covariance structures will be determined using
	Akaike's information criteria to evaluate the best model fit. Results
	analysis will be examined for both treatment effects and the Treatment
	x Time Block interaction results.
2. Subjects will report lower	Craving measures (AUQ and VAS) collected at 30-minute intervals
levels of craving as	during the self-administration trials will be used to test the effect of
measured by the Visual	lacosamide on alcohol craving. A mixed models approach will be used
Analog Scale (VAS) and the	to test for differences in craving between the lacosamide and placebo
Alcohol Urge questionnaire	self-administration trials. Within-subject factors for this analysis will
(AUQ) during the	include Treatment and Time Block. Trial order will be used as
lacosamide self-	covariate in these analyses to allow evaluation as to whether the order
administration trial	of treatments has a significant effect on the outcome.
compared to the placebo	
self-administration trial.	
3. There will be no	COWAT and Digit Span scores collected on the day of each self-
significant difference in	administration trial (prior to consumption) will be used to determine the
verbal fluency or working	effect of lacosamide on verbal fluency and working memory. A mixed
memory between trials of	model repeated measures approach will be used to test for differences
lacosamide and placebo.	in COWAT and digit span scores between the lacosamide trial and the

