12.2 Sample Size Determination

In our initial proposal a group size of 20 completers was selected for use in this study based on an assumed effect size of 1.00 suggested by similar alcohol self-administration studies with amount consumed as the primary outcome^{38,63}. This effect size is in the range we found for the anticonvulsant drug zonisamide used in an alcohol self-administration study³⁷. For an estimated reduction of 2.1 drinks with an estimated standard deviation (1.48) of the period differences for each participant with each sequence, effect size of this magnitude (1.00) requires a sample size of 20 that would allow for detection of a significant within-subject difference in alcohol consumption with an alpha value of 0.05 and power value of 0.8.

In response to reviewers' concerns about the need to detect a smaller than large effect size we determined the sample size need to detect a moderate effect size (f = 0.25). Assuming a correlation among repeated measures of 0.6 and that the assumption of compound symmetry holds, for comparison of total drinks obtained at 2 time points, for a power of 0.8, with an alpha value of 0.05, a sample size of 28 subjects would be needed for the detection of a moderate effect size. The power using this sample size will be greater than 0.8 if data for 4 time points are analyzed.

Given that this a laboratory based experiment we do not plan to conduct any planned interim analyses in this study.

13 Ethics/Protection of Human Subjects

This study is to be conducted according to applicable US federal regulations and institutional policies (which are based in federal regulations, guidance, and ICH Good Clinical Practice guidelines).

This protocol and any amendments will be submitted to the Boston Medical Center and Boston University Medical Campus IRB, for formal approval of the study conduct. The decision of the IRB concerning the conduct of the study will be made in writing to the investigator. A copy of the initial IRB approval letter will be provided to the sponsor before commencement of this study.

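### Drinking volume, VAS and AUQ are all primary with no testing order or success rule, while the trial is sized for one total-drinks test at 0.05; if any one measure may count, the false-positive chance is about 11–12% under plausible assumed correlations

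*Combined protocol and SAP*

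**What the plan says.** Section 4.1 sets a joint aim: "The specific objective of this study is to determine whether lacosamide has effects on alcohol craving and consumption". Section 4.2.1 carries it into the endpoints: "The primary outcomes are alcohol consumption and cravings during the alcohol self-administration trials". It then names drinking volume for consumption, and VAS and AUQ for craving, with no lead scale.

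Section 12.1 opens: "For our primary outcomes, separate analyses will be conducted on data collected during the Priming and Self-Administration periods of the test session". Hypothesis 1 is tested on volume, in two one-hour blocks, and the plan adds that the "analysis will be examined for both treatment effects and the Treatment" by Time Block interaction. Hypothesis 2 uses "Craving measures (AUQ and VAS) collected at 30-minute intervals" during self-administration. The hypotheses are numbered, but the numbering is not described as a testing order.

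Section 12.2 gives the only alpha for these outcomes, "for comparison of total drinks obtained at 2 time points, for a power of 0.8, with an alpha value of 0.05", and concludes that "a sample size of 28 subjects would be needed for the detection of a moderate effect size". Sections 2 and 3.2 say that success could lead to a phase II trial. No section defines success.

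**The concern.** Three primary measures analysed separately give up to three chances of a positive result, yet the stated alpha belongs to one of them. Whether the overall error is inflated depends on the success rule: any one measure, drinking or craving as a whole, or all three. The plan states none of these, so the rule could be chosen after the results are known.

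Hypotheses 1 and 2 both predict a reduction. The error that bears on the phase II decision is thus a false result in lacosamide's favour, nominally 2.5% for a single two-sided 0.05 test.

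**Working it through.** **Inputs.** From Section 12.2: f = 0.25, correlation 0.6 between repeated measures, 2 time points, alpha 0.05, power 0.8, n = 28. From Section 4.2.1: three primary measures. The 0.6 links repeated values of the same outcome, so it says nothing about how drinking, VAS and AUQ move together. Correlations between outcomes are assumed below and shown as a range.

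**1. The plan's own sample size.** Noncentrality = n × 2 × f² / (1 − 0.6), with 1 and n − 1 degrees of freedom.
- n = 28: 28 × 2 × 0.0625 / 0.4 = 8.75, power 0.814.
- n = 27: 8.44, power 0.798.

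So 28 is exactly the size for one two-sided test at 0.05. It contains no allowance for further primary tests.

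**2. Three independent tests, any one counting.** Two-sided: 1 − 0.95³ = 14.3%. In lacosamide's favour: 1 − 0.975³ = 7.3%.

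**3. Correlated tests.** These rates come from simulating 4,000,000 trivariate normal draws with no effect on any measure and a critical value of 1.96. Entries are percentages; *favour* means in lacosamide's favour.

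| Assumed correlations | Any one, two-sided | Any one, favour | Volume, or both scales: two-sided | Volume, or both scales: favour | All three, two-sided |
|---|---|---|---|---|---|
| Common 0 | 14.3 | 7.3 | 5.2 | 2.6 | 0.01 |
| Common 0.5 | 12.5 | 6.3 | 5.6 | 2.8 | 0.3 |
| Common 0.7 | 10.9 | 5.5 | 5.8 | 2.9 | 0.9 |
| Common 0.9 | 8.4 | 4.2 | 5.7 | 2.9 | 2.3 |
| VAS–AUQ 0.8, volume–craving 0.3 | 12.1 | 6.1 | 6.9 | 3.5 | 0.3 |
| VAS–AUQ 0.8, volume–craving 0.5 | 11.5 | 5.7 | 6.7 | 3.3 | 0.5 |
| VAS–AUQ 0.9, volume–craving 0.3 | 11.4 | 5.7 | 7.6 | 3.8 | 0.3 |
| VAS–AUQ 0.9, volume–craving 0.5 | 10.8 | 5.4 | 7.3 | 3.7 | 0.7 |

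The zero-correlation row can be checked by hand for the middle rule: 0.05 + 0.95 × 0.05² = 5.2%, and 0.025 + 0.975 × 0.025² = 2.6%. Repeating the any-one case with t tests on 28 within-subject differences gave 14.2% (correlation about 0), 12.5% (0.5), 8.5% (0.9) and 10.9–12.1% (unequal correlations).

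**4. Power under the possible rules.** If all three are required, the chance of success cannot exceed the 0.814 for total drinks at n = 28. How far below it lies cannot be computed, because Section 12.2 gives no craving inputs. If alpha is shared, power for total drinks at n = 28 is 0.658 at 0.05/3 and 0.718 at 0.025. At 0.05/3, power reaches 0.8 at n = 37 (0.808; n = 36 gives 0.794).

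**The case against.** The strongest reply is that three separate chances to win is the least favourable reading. Section 4.2.1 names two outcomes, and Hypothesis 2 is a single hypothesis about craving on both scales. Requiring both scales is at least as natural, and the favourable-direction error is then 2.6–3.8%, not far from 2.5%. This stands as a limit on the size of the problem. It does not remove the gap, since the plan does not state this rule either.

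Consumption also leads in practice. It is Hypothesis 1, it is the only outcome sized, and Section 12.2 says that comparable studies used amount consumed as primary. That supports putting it first, but the remark describes other studies and does not rank this trial's outcomes.

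A reader might infer that the error rate is simply 14%. That needs both an any-one rule and zero correlation among all three measures. Zero correlation is unlikely for two craving scales taken at the same times, and Section 3.1 reports that craving and drinking fell together in an earlier zonisamide study.

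A reader might also count the interaction and the Priming-period analyses as several more routes to success. The documents do not support that. Hypothesis 1 is a treatment contrast, which an interaction cannot establish. The priming drink is a fixed dose, and Appendix B schedules VAS but not AUQ in the observation period. The Priming analysis therefore adds at most one VAS test, and Hypothesis 2 is confined to self-administration.

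Finally, this is a laboratory screening study, and a false positive would lead to another controlled trial rather than a treatment claim. That lowers the stakes, but the study states an alpha and a power and still needs a success rule.

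**Conclusion.** The gap is real and should be fixed: three primary measures, separate analyses, and no ranking, adjustment or success rule, with a sample size that covers one test. Its size is conditional on the rule and on assumed correlations.

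- **Any one measure suffices:** 10.8–12.1% two-sided and 5.4–6.1% in lacosamide's favour under the more plausible unequal correlations. Over common correlations from 0.9 down to 0, it is 8–14% and 4–7%.
- **Craving needs both scales:** 5.2–7.6% two-sided and 2.6–3.8% in favour.
- **All three needed:** no inflation, but a rule for which the trial is not powered.

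The documents do not show that the any-one rule is intended. They leave the choice open.

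**What to change.** Before unblinding, amend Sections 4.2.1 and 12.1 as follows.

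1. Make the treatment main effect on total drinks (blocks 1 and 2 together) the first primary test, at two-sided 0.05.
2. Test VAS and AUQ in a fixed order set in advance, each at 0.05 and only if the preceding test succeeds. Either order of the scales will do.
3. Label the Treatment by Time Block interaction and the Priming-period analysis (in practice VAS only) as supportive.

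This holds the family-wise error at 5% whatever the correlations, and power for total drinks stays at 0.814 with 28 subjects. The cost is one of substance: craving is placed behind drinking although Section 4.1 makes them joint aims, and a craving effect could not be confirmed if drinking is not significant.

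If the sponsor wants craving to be able to succeed alone, there are two options: apply Holm's procedure over the three measures, or name one craving scale and apply Holm over two outcomes. Power for total drinks at n = 28 should then be restated; the worst cases are 0.658 (first step at 0.0167) and 0.718 (first step at 0.025).

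That cost depends on how many subjects are analysed. The Protocol Summary says "The present study will involve 112 men and women aged 21 to 55 who exceed safe levels of drinking". If all 112 were analysed, power at 0.0167 would exceed 0.99 under the Section 12.2 inputs, but the documents do not say how many are expected to complete.
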